#### 10. INTERIM ANALYSES

An interim futility analysis is planned when the first 50 participants (Group A and Group B combined) have been evaluated for response or have permanently discontinued study treatment because of disease progression, withdrawal of consent, or death. The study will be terminated for futility if  $\leq 18$  of the 50 participants have responded (ie, CR or PR) based on assessments provided by the IRC; otherwise the study will continue. The probability of stopping at interim for futility is 62.16% when the true response rate is 35% or 2.34% when the true response rate is 51%.

An IDMC will be charged with evaluating interim futility results. The IDMC will consist of clinicians and an independent statistician. The IDMC will make recommendations to the sponsor at the planned interim futility analysis. The process by which the IDMC will make recommendations and decisions will be documented in the IDMC charter. Additional operational details of the interim analyses, including tables, figures, and listings provided to the IDMC, will be provided in the IDMC Charter.

There is no efficacy interim analysis planned for the study.

#### 11. CHANGES AND MODIFICATIONS TO THE ANALYSIS PLAN

All versions of the SAP are listed in Table 6.

**Table 6: Statistical Analysis Plan Versions** 

SAP Version	Date
Original	01 MAR 2019
Amendment 1	26 AUG 2020
Amendment 2	28 JAN 2021

# 11.1. Changes to Protocol-Defined Analyses

The PP population was removed from the planned analysis. For a single-arm, open-label study, the determination of participants to be excluded from the PP population is post hoc and may not be done objectively; thus, analysis based on this population may not be meaningful.

# 11.2. Changes to the Statistical Analysis Plan

**Amendment 2 (28 JAN 2021)** 

**Overall Rationale for the Amendment:** The primary purpose of this amendment is to comply with responses to comments provided by FDA regarding the Statistical Analysis Plan Amendment 1.

- Section 6.4 was updated to include the summary for the number of dose reductions and the number of dose interruptions of each participant.
- Section 7.3.1 was updated to include a sensitivity analysis of ORR that summarizes participants who switched to the selected dose after starting the maintenance dose in a separate treatment regimen and to include an additional analysis on the number of participants who achieved best overall response after the time of crossover along with the best overall response data for this separate treatment regimen.
- Section 7.4.1 was updated to include a sensitivity analysis of CRR by summarizing participants who switched to the selected dose after starting the maintenance dose in a separate treatment regimen.
- Section 7.4.2 and Section 7.4.3 were updated to included sensitivity analyses where response assessments after the time of crossover will be excluded from the determination of DOR and PFS for participants who switched to the selected treatment regimen after starting the maintenance dose.
- Section 9.2.1 was modified to clarify how AEs that occur after new anti-lymphoma therapy will be assessed.
- **Incorporation of minor changes.** Other minor changes have been incorporated throughout the SAP and are noted in the redline version of the amendment.

#### **Amendment 1 (26 AUG 2020)**

- Section 3 was modified to increase the target enrollment from approximately 100 to approximately 120 participants. This change is to align with recommendations from FDA.
- Section 4.1.4 was updated to include details of rules for handling partial/missing onset or end date of TEAEs in the calculation of time to onset or duration of a TEAE. Rules for partial/missing date of last dose were updated to include details for when both month and day are missing.
- Section 5.2 was modified to provide details regarding how crossover participants will be summarized.
- Section 5.3 was updated to add the all-screened population for the summary of analysis populations.
- Section 6.1.2 was updated to add relapsed/refractory status to the most recent prior therapy to the summary table of disease history because the response to last regimen before entering the study may be a prognostic factor for clinical outcomes.
- Section 6.2 was modified to add summaries of participants who are ongoing with treatment or still in the study.
- Section 6.4 was modified to change the calculations of duration of treatment and average dose during the maintenance dosing period because Group B with 2.5 mg QD was selected as the maintenance dose.
- Section 7.3 was updated to change the timing of the primary analysis to align with recommendations from FDA.
- Section 7.3.2 was modified to add "unknown" as a category for bone marrow involvement at baseline. Relapsed/refractory status to the most recent prior therapy was added to the subgroup analysis because the response to last regimen before entering the study may be a prognostic factor for clinical outcomes.
- Section 7.4.3 was modified to update references of censoring for PFS.
- Section 9.2.2 was updated to include details of analyses on time to onset of selected TEAEs of special interest. Summaries of longest duration of selected TEAEs of special interest were added to have a better understanding of the safety profile in terms of duration of class-effect AEs as well as AEs influenced by treatment regimens. "Grade 2 or higher" was changed to "Grade 3 or higher" for time to onset summary of rash. This change was made to be consistent with other PI3K inhibitors, which highlighted more severe cutaneous reactions graded as Grade 3 or higher in the labeling. "Herpes simplex virus infection" was changed to "herpes simplex" based on the MedDRA coding dictionary as a broader term. Exfoliative dermatitis was added to the list of TEAEs of special interest.

- Section 9.2.3 was updated to include summary of TEAEs by PT and maximum severity in decreasing order of frequency, summary of longest duration of selected TEAEs of special interest, and additional supporting summaries during the INCB050465 initial QD dosing period and the maintenance dosing period, which will provide supportive data of the safety profile of the maintenance dose. Summary of nonserious TEAEs by SOC and PT was removed because it will not be used for the clinical study report but will be provided for result disclosure.
- Section 9.3.2 was modified to include ALT and AST in the line graphs as additional supportive analyses for laboratory events of special interest.
- Section 9.3.3 was added to identify potential Hy's law events to better monitor liver toxicity.
- Section 9.3.4 was updated to align with the analysis plan for adverse events of special interest. Summary of worsening of laboratory events of special interest was removed because this is covered by the summary of worsening of laboratory abnormalities.
- Section 9.5 was updated to change the high threshold of QTcF and QTcB interval from 460 to 450 milliseconds for purpose of analysis. This change is to comply with the categories outlined in FDA Guidance for Industry (E14 Clinical Evaluation of QT/QTc Interval Prolongation and Proarrhythmic Potential for Non-Antiarrhythmic Drugs) used to characterize outliers in OTc values.

#### APPENDIX A. PLANNED TABLES, FIGURES, AND LISTINGS

This appendix provides a list of the planned tables, figures, and listings for the Clinical Study Report. Standard tables will follow the conventions in the Standard Safety Tables v1.9. Shells are provided for nonstandard tables in a separate document.

The lists of tables, figures, and listings and the shells are to be used as guidelines. Modifications of the lists that do not otherwise affect the nature of the analysis will not warrant an amendment to the SAP.

#### **Tables**

Table No.	Title	Population	Standard	
Baseline an	Baseline and Demographic Characteristics			
1.1.1	Analysis Populations	All-Screened	X	
1.1.2	Summary of Participant Disposition	FAS	X	
1.1.3	Summary of Number of Participants Enrolled by Country and Site	FAS	X	
1.1.4	Summary of Protocol Deviations	FAS	X	
1.2.1	Summary of Demographics and Baseline Characteristics	FAS	X	
1.3.1	Summary of Baseline Disease Characteristics	FAS	X	
1.3.2	Summary of Prior Cancer Therapy	FAS		
1.3.3	Summary of Prior Systematic Cancer Therapy by WHO Drug Class and Preferred Term	FAS		
1.4.1	Summary of Prior Medications	FAS	X	
1.4.2	Summary of Concomitant Medications	FAS	X	
1.5.1	Summary of General Medical History	FAS	X	
Efficacy				
2.1.1	Summary of Best Overall Response and Objective/Complete Response Rate as Determined by Independent Review Committee	FAS		
2.1.2	Summary of Best Overall Response and Objective/Complete Response Rate as Reported by Investigator	FAS		
2.1.3	Summary of Best Overall Response and Objective Response Rate as Determined by Independent Review Committee by Subgroup	FAS		
2.2.1	Summary of Duration of Response as Determined by Independent Review Committee	FAS		
2.2.2	Summary of Duration of Response as Reported by Investigator	FAS		
2.2.3	Summary of Progression-Free Survival as Determined by Independent Review Committee	FAS		
2.2.4	Summary of Progression-Free Survival as Reported by Investigator	FAS		
2.2.5	Summary of Overall Survival	FAS		
2.2.6	Summary of Best Change in Target Lesion Size as Determined by Independent Review Committee	FAS		
2.2.7	Summary of Best Change in Target Lesion Size as Reported by Investigator	FAS		

Table No.	Title	Population	Standard
2.4.1	Summary of Best Overall Response and Objective/Complete Response Rate as Determined by Independent Review Committee – Crossover as a Separate Treatment Group	FAS	
2.4.2	Summary of Best Overall Response and Objective/Complete Response Rate as Reported by Investigator – Crossover as a Separate Treatment Group	FAS	
2.4.3	Summary of Best Overall Response as Determined by Independent Review Committee for Crossover Participants	FAS	
2.4.4	Summary of Best Overall Response as Reported by Investigator for Crossover Participants	FAS	
2.4.5	Summary of Duration of Response as Determined by Independent Review Committee – Censoring Crossover Participants	FAS	
2.4.6	Summary of Duration of Response as Reported by Investigator – Censoring Crossover Participants	FAS	
2.4.7	Summary of Progression-Free Survival as Determined by Independent Review Committee – Censoring Crossover Participants	FAS	
2.4.8	Summary of Progression-Free Survival as Reported by Investigator – Censoring Crossover Participants	FAS	
Safety			
3.1.1	Summary of Exposure and Compliance	Safety	
3.1.2	Summary of Exposure and Average Daily Dose During Initial QD Dosing Period	Safety	
3.1.3	Summary of Exposure and Average Daily Dose During Maintenance Dosing Period	Safety	
3.2.1	Overall Summary of Treatment-Emergent Adverse Events	Safety	X
3.2.2	Summary of Treatment-Emergent Adverse Events by MedDRA System Organ Class and Preferred Term	Safety	X
3.2.3	Summary of Treatment-Emergent Adverse Events by MedDRA Preferred Term in Decreasing Order of Frequency	Safety	X
3.2.4	Summary of Treatment-Emergent Adverse Events by MedDRA System Organ Class, Preferred Term, and Maximum Severity	Safety	X
3.2.6	Summary of Grade 3 or Higher Treatment-Emergent Adverse Events by MedDRA System Organ Class and Preferred Term	Safety	X
3.2.7	Summary of Grade 3 or Higher Treatment-Emergent Adverse Events by Preferred Term in Decreasing Order of Frequency	Safety	X
3.2.8	Summary of Serious Treatment-Emergent Adverse Events by MedDRA System Organ Class and Preferred Term	Safety	X
3.2.9	Summary of Serious Treatment-Emergent Adverse Events by Preferred Term in Decreasing Order of Frequency	Safety	X
3.2.10	Summary of INCB050465 Treatment-Related Treatment-Emergent Adverse Events by MedDRA System Organ Class and Preferred Term	Safety	X
3.2.11	Summary of INCB050465 Treatment-Related Treatment-Emergent Adverse Events by MedDRA Preferred Term in Decreasing Order of Frequency	Safety	X

Table No.	Title	Population	Standard
3.2.12	Summary of INCB050465 Treatment-Related Treatment-Emergent Adverse Events by MedDRA System Organ Class, Preferred Term, and Maximum Severity	Safety	X
3.2.14	Summary of Grade 3 or Higher INCB050465 Treatment-Related Treatment-Emergent Adverse Events by MedDRA System Organ Class and Preferred Term	Safety	X
3.2.15	Summary of INCB050465 Treatment-Related Serious Treatment- Emergent Adverse Events by MedDRA System Organ Class and Preferred Term	Safety	X
3.2.16	Summary of Treatment-Emergent Adverse Events With a Fatal Outcome by MedDRA System Organ Class and Preferred Term	Safety	X
3.2.18	Summary of Treatment-Emergent Adverse Events Leading to INCB050465 Dose Reduction by MedDRA System Organ Class and Preferred Term	Safety	X
3.2.19	Summary of Treatment-Emergent Adverse Events Leading to INCB050465 Dose Interruption by MedDRA System Organ Class and Preferred Term	Safety	X
3.2.20	Summary of Treatment-Emergent Adverse Events Leading to Discontinuation of INCB050465 by MedDRA System Organ Class and Preferred Term	Safety	X
3.2.25	Summary of Treatment-Emergent Adverse Events by MedDRA Preferred Term and Maximum Severity in Decreasing Order of Frequency	Safety	
3.2.26	Summary of Selected Treatment-Emergent Adverse Events of Special Interest by Maximum Severity	Safety	
3.2.27	Summary of Time to Onset of Selected Treatment-Emergent Adverse Events of Special Interest	Safety	
3.2.28	Summary of Time to Onset of Selected Treatment-Emergent Adverse Events of Special Interest: Life-Table Method	Safety	
3.2.29	Summary of Longest Duration of Selected Treatment-Emergent Adverse Events of Special Interest	Safety	
3.3.1.1	Summary of Laboratory Values - Hematology	Safety	X
3.3.1.2	Summary of Laboratory Values - Chemistry	Safety	X
3.3.3.1	Shift Summary of Hematology Laboratory Values in CTC Grade - To the Worst Abnormal Value	Safety	X
3.3.3.2	Shift Summary of Chemistry Laboratory Values in CTC Grade - To the Worst Abnormal Value	Safety	X
3.3.3.4	Treatment-Emergent Worsening of Laboratory Abnormalities - Hematology	Safety	X
3.3.3.5	Treatment-Emergent Worsening of Laboratory Abnormalities - Chemistry	Safety	X
3.3.6	Time to Onset of Treatment-Emergent Worsening of Laboratory Events of Special Interest	Safety	
3.3.7	Time to Onset of Treatment-Emergent Worsening of Laboratory Events of Special Interest: Life-Table Method	Safety	
3.4.1	Summary of Systolic Blood Pressure	Safety	X
3.4.2	Summary of Diastolic Blood Pressure	Safety	X
3.4.3	Summary of Pulse	Safety	X
3.4.4	Summary of Respiratory Rate	Safety	X
3.4.5	Summary of Body Temperature	Safety	X
3.4.6	Summary of Weight	Safety	X

Table No.	Title	Population	Standard
3.5.1	Summary of PR Interval (ms) From 12-Lead ECG	Safety	X
3.5.2	Summary of QRS Interval (ms) From 12-Lead ECG	Safety	X
3.5.3	Summary of QT Interval (ms) From 12-Lead ECG	Safety	X
3.5.4	Summary of QTcB Interval (ms) From 12-Lead ECG	Safety	X
3.5.5	Summary of QTcF Interval (ms) From 12-Lead ECG	Safety	X
3.5.6	Summary of RR Interval (ms) From 12-Lead ECG	Safety	X
3.5.8	Summary of Outliers of QT, QTcB, and QTcF Interval Values From 12-Lead ECG	Safety	X
3.5.9	Summary of Clinically Significant ECG Abnormality	Safety	X

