1.4. Study Rationale

The PI3K δ inhibitor idelalisib was approved for the treatment of patients in the United States with relapsed follicular B-cell NHL who have received at least 2 prior systemic therapies. In September of 2017 the PI3K inhibitor copanlisib was also approved in the United States for the same patient population (Aliqopa 2017). Idelalisib was approved in the European Union for the treatment of adult patients with FL that is refractory to 2 prior lines of treatment. The population of patients that are refractory to 2 lines of systemic therapy is substantially smaller than the population that has relapsed or refractory disease after 2 prior systemic therapies. The relapsed patient population is currently underserved by the available approved therapies and, like the double-refractory population, represents an unmet medical need. This is especially true in patients that are ineligible for HSCT. To address the unmet medical need of both populations, and to enroll the study in a timely fashion, the study will allow subjects who have either relapsed or refractory disease after at least 2 prior systemic therapies and who are ineligible for HSCT. INCB050465 is a potent and selective PI3K δ inhibitor and has demonstrated rapid and deep objective responses in subjects with relapsed FL (see Section 1.3).

This study is designed to evaluate the ORR of INCB050465 in subjects with relapsed or refractory FL who have received at least 2 prior systemic therapies and who are ineligible for HSCT. Given that copanlisib was recently granted accelerated approval in this patient population on the basis of ORR by the US FDA, idelalisib can no longer be considered the standard of care in the United States and consequently is not a relevant comparator for new PI3K inhibitors. It is also not feasible to replace idelalisib with copanlisib, which is currently approved only in the United States. Study INCB 50465-203 will therefore evaluate only INCB050465.

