13. Current or previous other malignancy within 3 years of study entry, except cured basal or squamous cell skin cancer, superficial bladder cancer, prostate intraepithelial neoplasm, carcinoma *in situ* of the cervix, or other noninvasive or indolent malignancy without sponsor approval.
14. History of stroke or intracranial hemorrhage within 6 months of the date of study treatment administration.
15. Chronic or current active infectious disease requiring systemic antibiotics, antifungal, or antiviral treatment, and exposure to a live vaccine within 30 days of study treatment administration.
16. Known human immunodeficiency virus (HIV) infection or positivity on immunoassay. Note: HIV screening test is optional for subjects enrolled in the United States, but subjects with known HIV infection in the United States will be excluded.
17. Hepatitis B (HBV) or hepatitis C (HCV) infection: Subjects positive for hepatitis B surface antigen (HBsAg) or hepatitis B core antibody will be eligible if they are negative for HBV-DNA; these subjects should be considered for prophylactic antiviral therapy. Subjects positive for anti-HCV antibody will be eligible if they are negative for HCV-RNA.
18. Clinically significant cardiac disease, including unstable angina, acute myocardial infarction, and or cardiac conduction issues within 6 months of the date of study treatment administration.
19. Current New York Heart Association Class II to IV congestive heart failure or uncontrolled arrhythmia.
20. Presence of an abnormal ECG that is clinically meaningful. Screening QTc interval > 450 milliseconds is excluded (corrected by Fridericia). In the event that a single QTc is > 450 milliseconds, the subject may enroll if the average QTc for 3 ECGs is < 450 milliseconds.
21. Unable to swallow and retain oral medication, malabsorption syndrome, disease significantly affecting gastrointestinal function, total resection of the stomach or small bowel, ulcerative colitis, symptomatic inflammatory bowel disease, or partial or complete bowel obstruction.
22. Known hypersensitivity or severe reaction to INCB050465 (**IB**) or any of the excipients.
23. History of serious allergic reactions including anaphylaxis and toxic epidermal necrolysis.

24. Inadequate recovery from toxicity and/or complications from a major surgery before study treatment administration.
25. Currently pregnant or breastfeeding.

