# 9.5. Electrocardiograms

Twelve-lead ECGs including PR, QRS, QT, QTcB, QTcF, and RR intervals will be obtained for each participant during the study. Values at each scheduled visit, change, and percentage change from baseline will be summarized for each ECG parameter. Baseline will be determined as the average of all nonmissing values before the first administration of INCB050465.

Normal ranges for ECG values are defined in Table 5. Electrocardiogram values will also be considered abnormal if the absolute percentage change from baseline is more than 25% (30% for QRS interval). Participants exhibiting ECG abnormalities will be listed with study visit and assigned treatment regimen. Abnormal values for participants with alert ECG values, defined as both the absolute value and the percentage change from baseline being outside normal ranges, will be identified and listed. Outliers of QT, QTcB, and QTcF values, defined as absolute values > 450 milliseconds or change from baseline > 30 milliseconds, will be summarized.

**Table 5:** Normal Ranges for Electrocardiogram Values

Parameter	High Threshold	Low Threshold
PR	≤ 220 ms	≥ 75 ms
QRS	≤ 120 ms	≥ 50 ms
QT	≤ 500 ms	≥ 300 ms
QTcB, QTcF	≤ 450 ms	≥ 295 ms
RR	≤ 1330 ms	≥ 600 ms

QTcB = Bazett's correction; QTcF = Fridericia's correction.

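### The SAP's ECG outlier definition puts no baseline condition on the 450 ms criterion, and because entry limits only QTcF, an eligible participant can meet it on QTcB with no change on treatment.

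*SAP*

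**What the plan says.** SAP 9.5 gives the rule: "Outliers of QT, QTcB, and QTcF values, defined as absolute values > 450 milliseconds or change from baseline > 30 milliseconds, will be summarized". The two criteria are joined by an or. The absolute criterion has no condition on the baseline value, and the sentence does not restrict it to postbaseline values. Baseline is defined in the same section ("Baseline will be determined as the average of all nonmissing values before the first administration of INCB050465"), but within the outlier rule it enters only the change criterion.

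The output is Table 3.5.8 in SAP Appendix A, "Summary of Outliers of QT, QTcB, and QTcF Interval Values From 12-Lead ECG", for the safety population. It is marked as a standard table. The appendix opening says that standard tables follow a separate conventions document, which is not among the protocol and SAP.

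Protocol 3.2, exclusion 20, sets the entry limit: "Screening QTc interval > 450 milliseconds is excluded (corrected by Fridericia". It adds that, after a single high reading, "the subject may enroll if the average QTc for 3 ECGs is < 450 milliseconds". It also excludes "Presence of an abnormal ECG that is clinically meaningful", with no number attached. Protocol 7.5.4 repeats the Fridericia basis for screening. Neither document sets an entry limit for QTcB. Protocol Table 11 lists QTcF only; SAP Table 5 adds QTcB at the same 450 ms limit.

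There is no control arm. Protocol 1.4 says: "Study INCB 50465-203 will therefore evaluate only INCB050465".

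**The concern.** An outlier table is useful mainly for showing who moved above a threshold after starting the drug. The 450 ms criterion as written does not separate that from who was above it already. For QTcF the gap is small, because exclusion 20 keeps most baselines at or below 450 ms. For QTcB nothing at entry does the same.

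In a controlled trial, participants already above the limit would appear in both arms and could be allowed for. Here all participants receive INCB050465, so a QTcB count could mix pre-existing and new exceedances with nothing to show the proportion. At stake is the interpretation of one descriptive safety table. No efficacy result, error rate or decision rule depends on it.

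**Working it through.** The documents state no figure for this point, so there is none to reproduce. The check is whether someone who passes the QTcF screen can have QTcB above 450 ms before dosing.

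**Inputs from the documents.** Entry limit QTcF 450 ms (Protocol 3.2, exclusion 20). Outlier limit above 450 ms for QTcB (SAP 9.5). Normal pulse range 45 to 100 bpm (SAP Table 4). Planned enrolment about 120 (SAP 3).

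**Relation between the corrections.** With RR in seconds, RR = 60 / heart rate:

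- Bazett: QTcB = QT / RR^(1/2)
- Fridericia: QTcF = QT / RR^(1/3)
- Dividing: QTcB = QTcF × RR^(-1/6)

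The factor is 1 at 60 bpm and rises with heart rate.

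| Heart rate (bpm) | RR^(-1/6) | QTcF at which QTcB reaches 450 ms | QTcB when QTcF is 450 ms |
|---|---|---|---|
| 60 | 1.000 | 450.0 | 450.0 |
| 70 | 1.026 | 438.6 | 461.7 |
| 80 | 1.049 | 428.9 | 472.1 |
| 90 | 1.070 | 420.6 | 481.5 |
| 100 | 1.089 | 413.3 | 490.0 |

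**Worked case.** QTcF 430 ms at 80 bpm: 430 × 1.0491 = 451.1 ms. This participant satisfies the QTcF limit with a pulse inside the SAP's normal range. If QT and heart rate stay the same on treatment, the change is 0 ms, but the absolute value is still above 450 ms and the definition is met.

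**How many.** The documents give no baseline QTcF, QTcB or heart-rate data, so every figure below is an assumption. QTcF and heart rate were simulated as independent normal variables and participants with QTcF above 450 ms were removed. The result is the share with pre-dose QTcB above 450 ms.

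| Assumed QTcF mean, SD (ms) | Assumed heart rate mean, SD (bpm) | Share | Of 120 |
|---|---|---|---|
| 400, 15 | 68, 11 | 1.2% | 1.5 |
| 405, 15 | 70, 12 | 3.3% | 4.0 |
| 405, 18 | 70, 11 | 4.6% | 5.5 |
| 415, 18 | 80, 11 | about 22% | about 26 |
| 425, 15 | 80, 12 | 37.0% | 44.4 |

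The share is above zero in every scenario tried, but it varies about thirtyfold (37.0 / 1.2 = 31). The inputs determine the result.

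**Comparison within the SAP.** SAP 9.3.2 presents laboratory grades as shifts from baseline to worst postbaseline grade, and SAP 9.3.4 times the first grade worse than baseline. The alert ECG values in SAP 9.5 need both an out-of-range value and an out-of-range percentage change. The outlier rule has no equivalent condition on its absolute criterion, and Appendix A lists no ECG shift table.

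**The case against.** The strongest objection is that the layout of Table 3.5.8 cannot be seen. It is a standard table, and its conventions may already restrict it to postbaseline values, split by baseline, or put the two criteria on separate rows. The or in SAP 9.5 says which values qualify, not that they share one row. This stands. A reader might infer that the table will in fact report pre-existing exceedances as drug-related outliers. The documents support only that the SAP text states no condition to prevent it.

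Second, other outputs mitigate the gap. QTcB values and changes are summarised by visit (Table 3.5.4), the 30 ms criterion is relative to baseline, alert values have their own listing (2.10.3), and Listing 2.10.1 gives ECG values, from which baseline status can be recovered. QTcF appears in the same table and is the only correction used for eligibility. This also largely stands. What is missing is a planned count of new crossings, which a reader would have to build from listings.

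Third, the 450 ms limit was deliberate: SAP 11.2 says it follows the categories in the cited guidance. That is accepted. The threshold is not in question, only the lack of a baseline split.

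Fourth, the scenario shares say nothing about this trial's data. A reader might take one of them, such as 6 to 26 of 120, as the inflation of the outlier count. The documents do not support that. The shares rest wholly on assumed distributions, and they count pre-dose values. Some of those participants may have no later value above 450 ms, and others would qualify through the 30 ms criterion anyway.

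**Conclusion.** The point holds as a gap in the SAP text. The 450 ms criterion in SAP 9.5 has no baseline condition, entry limits only QTcF, and at any heart rate above 60 bpm an eligible participant can have QTcB above 450 ms before dosing and meet the definition unchanged. That much follows from the documents and the two correction formulas, with no distributional assumption.

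The size cannot be derived. About 1% to 37% with pre-dose QTcB above 450 ms is a range over assumed QTcF and heart-rate distributions taken as independent. It is not an estimate for this trial, and it does not measure inflation of the reported count. The consequence is confined to the reading of one descriptive safety table, and the standard-table conventions may already deal with it. This is a cheap improvement of low severity.

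**What to change.** In SAP 9.5, as applied in Table 3.5.8, for each of QT, QTcB and QTcF:

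- For the absolute criterion, report participants with baseline at or below 450 ms and at least one postbaseline value above 450 ms, over participants with baseline at or below 450 ms.
- Show the number with baseline above 450 ms on its own row.
- Report the change of more than 30 ms from baseline on its own row.

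If the standard table already does this, one sentence in SAP 9.5 confirming it is enough.

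The cost is a sentence in the SAP and a table footnote. No new data are needed. The downside is a smaller denominator for the absolute criterion, mainly for QTcB: slight if few participants start above 450 ms, and visible from the separate baseline row in any case.
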